7.2. Sample size

As this is an exploratory study no formal sample size calculation has been performed. It is assumed that 10 subjects with spinal cord injury, 10 subjects with enlarged prostate and 10 healthy volunteers will be adequate for the characterization.

7.3. Level of significance and power

If explorative statistical analyses are performed a significance level of 5% will be applied.

7.4. Drop-out

Due to the exploratory nature of the study, drop-out subjects will not be replaced.

7.5. Pass/fail criteria

No formal pass/fail criteria are applied in this explorative pilot evaluation.

7.6. Interim analysis

No interim analysis will be performed.

7.7. Statistical reason for termination of investigation

There is no reason to terminate the investigation based on statistical considerations.

7.8. Deviation(s) from statistical plan

Any deviations from the statistical plan will be documented in the clinical report.

8. Data management

8.1. Data review, database cleaning, and issuing and resolving data queries

Data management and statistical analyses is carried out by the Medical Affairs, Coloplast A/S.

To ensure correct data entry, data is entered twice (double data entry). Data management is responsible for control of data consistency and for completeness of data from each subject.

Discrepancies are listed in Data Query Forms (DQF), and the Investigator is responsible for solving these promptly. When all DQFs are solved the database is locked and the statistical analyses are performed.

8.2. Verification, validation and securing of electronic clinical data systems

EXPeRT Data Management, version 5.0.05 system delivered by OmniComm Systems Inc. is used for data management. The system is designed to be compliant with the requirements of 21 CFR part 11. It is a validated data management system allowing only qualified and trained personnel to enter the system.

8.3. Data retention

The sponsor file must be archived for a minimum period of 5 years after the final clinical investigation report has been signed.

All investigation site documents must be archived for a minimum period of 5 years after the final clinical investigation report has been signed. The monitor is responsible for informing the investigator and the CM if this period should be longer for their sites per local regulation.

9. Amendments to the CIP

Any significant changes to the CIP are:

- Agreed between sponsor and Principal Investigator(PI).
- Justified in a statement included in the amended section and the version number and date of amendment must be documented.
- Registered in the Change Log.
- Notified and approved by the EC before implementation.

Example of significant change: Changes of inclusion criteria, end points or assessment methods.

10. Clinical Investigation Plan deviations / violations

10.1. Deviations

Deviations to Clinical Investigation Plan occurs when the activities during the clinical investigation diverge from the EC approved investigation plan.

A deviation does not increase risk or decrease benefit or; does not have a significant effect on the subject's rights, safety or welfare; and/or on the integrity of the data.

Examples of deviations:

- Vital signs obtained prior to informed consent
- Urine dipstick is completed, but not sent for formal urine analysis
- Partly completing required tests

The Investigator is not allowed to deviate from the CIP unless under emergency circumstances and to protect the rights, safety and well-being of the subject(s).

Deviations must be reported to sponsor and deviations affecting the scientific aspect of the investigation or the safety of the subject are reported to the EC by sponsor.

10.2. Violations

Violations to the Clinical Investigation Plan occurs when there is divergence from the EC approved investigation plan (a deviation) that also:

- Reduces the quality or completeness of the data
- Impacts a subject's safety, rights or wellbeing
- Affects the scientific integrity

Examples of violations:

- Inadequate informed consent
- Enrolment of subjects not meeting the inclusion / exclusion criteria
- Initiation of study procedure prior to completion of informed consent
- Unreported SAE's
- Repeated deviations of the same nature
- Falsification

If any deviations and/or violations to the investigation plan are detected, the Clinical Manager will complete a Deviation/Violation Form and inform/discuss with the Principal Investigator immediately.

In case of continued or repeated violations affecting the scientific aspect of the investigation or the subjects' rights, safety and well-being sponsor will disqualify the PI from further participation in the investigation.

The Clinical Manager must report all violations detected during a monitoring visit in the Periodic Monitoring Report.

11. Statement of compliance

The clinical investigation is conducted in accordance to:

- Ethical principles that have their origin in "The Declaration of Helsinki, 1964, last amended at the 64th WMA General Assembly, Brazil, October 2013".
- MDD 93/42/EEC as amended by Directive 2007/47/EC (commonly known as the Medical Device Directive).
- ISO 14155:2011 "Clinical Investigation of medical devices for human subjects – Good clinical practices".
- Any applicable regional or national regulations will be specified in the country specific CIP.

11.1. Ethics committee and regulatory authorities

The CIP and/or other relevant documents are submitted to the appropriate EC. This clinical investigation will not begin until the required approval from the EC has been obtained. Any amendment to the protocol will be submitted to the same EC.

Sponsor will notify the EC concerned of the end of the clinical investigation.

11.2. Data protection

This clinical investigation does not require approval by the Data Protection Agency. Per the Order 410 of 09/05/2012, Exemption from submission to the Data Protection Agency, handling of sensitive personal data in health science research projects is exempted from the requirement for notification and permission from the Data Protection Agency if the project is covered by the Act on Scientific Ethics of Health Science Research Projects and is authorized by a Scientific Committee.

Coloplast A/S is committed to and follows the Data Protection Act. All information collected during this investigation is kept strictly confidential. Subjects are identified by an investigation number and the investigation monitor has limited access to subjects' documentation for source data verification. Any information which could identify a subject remains with the investigator where it is archived with investigation documents. Subjects remain anonymous for data analysis.

Should the investigation require future review, relevant regulatory authorities and ethics committees will be allowed access to all relevant information for audit and inspection purposes.

11.3. Indemnity

All subjects are fully covered by Coloplast A/S insurance throughout the investigation:

[REDACTED]

11.4. Financial conditions

Coloplast A/S will compensate investigator and study nurses for their time and resources spent on the investigation (including overhead for the hospital and administrative costs) as specified in a sponsor investigator

contract. Investigator fee, including subject remuneration, is estimated up to [REDACTED]. Investigator has no apparent conflict of interest.

Subjects will be remunerated with a voucher equal to [REDACTED] per completed visit equal to two (2) vouchers per subject upon completion of the investigation. This is to compensate for any inconvenience caused during the catheterisations, time used and travel expenses.

12. Informed consent process

Written informed consent is obtained from all subjects participating in the investigation after thorough written and verbal information. The informed consent process takes place in a room reserved for ensuring privacy and quiet surroundings at the investigator's department. The subjects will receive both written and verbal information about the possibility of bringing a companion to the visit and to any possible subsequent visits.

The information is given by the investigator or his/her representative in the subjects' native non-technical language. Each subject will be fully informed about the aim of the investigation, procedures, potential risks or inconveniences and/or expected benefits and have a minimum of 24 hours before deciding on participation. If the subject wishes to consent immediately after receiving information, he may do so and in- and exclusion may be initiated.

The subjects will be informed that their participation is voluntary and that they may leave the investigation at any time, without this having any influence on their further treatment.

The informed consent signature form includes personally dated signatures of the subject and the PI or his/hers representative responsible for conducting the informed consent process. A copy will be provided to the subject.

If new information is to be given during the investigation, sponsor will inform the investigators, and the new information is given to the subjects by the investigator. If new information becomes available that can significantly affect a subject's future health and medical care that information will be provided to the subject in written form. CM is responsible for writing the information and providing it to investigators that will further provide it to the subjects. If applicable, all affected subjects shall be asked to confirm their continuing informed consent in writing.

This procedure also applies to informed consent obtained from a subject's legal representative. The procedure cannot waive the subjects' legal rights.

13. Adverse events, serious adverse events and device deficiencies

13.1. Adverse events

An adverse event is any untoward medical occurrence, unintended disease or injury, or untoward clinical signs (including abnormal laboratory findings) in subjects, users or other parties, whether related to the medical device(s), or the procedures involved or not. This could include events such as headache or dizziness.

13.2. Adverse device effect

An adverse event, which is related to the use of the medical device, is an adverse device effect, and should be marked as related or possibly related on the adverse event form.

The definition of an adverse device effect includes any event resulting from insufficiencies or inadequacies in the instruction for use, malfunction of the device, use error or from intentional misuse of the device.

Although not testing a medical device in this investigation, several procedures include use of CE-marked medical devices (e.g. catheters for urodynamic examinations).

ANTICIPATED ADE RELATED TO URODYNAMIC PROCEDURES	INCIDENCE RATE SCI/BPH PTS	INCIDENCE RATE HEALTHY VOLUNTEERS
Urinary tract infection	Unlikely	Very unlikely
Macroscopic haematuria	Unlikely	Unlikely
Stinging and pain in urethra during examination	Likely	Likely

Table 6 Anticipated adverse device effects and their likely incidence rates.

Incidence rates for patients are based on literature data (2, 3) while rates for healthy volunteers are based on data from a clinical study (4). Definition of incidence rates are based on Coloplast risk management system (very unlikely 0-1%, unlikely 2-10%, occasional 11-50%, likely 51-90%, very likely 91-100%).

13.3. Device deficiency

A device deficiency is the inadequacy of the medical device with respect to its identity, quality, durability, reliability, safety or performance. This includes malfunctions, misuse or use errors and inadequate labelling.

13.4. Serious adverse events

A serious adverse event is an adverse event that:

- Led to Death,
- Led to a serious deterioration in health of the subject that either resulted in:
 - 1) a life-threatening illness or injury, or
 - 2) a permanent impairment of a body structure or a body function, or
 - 3) required in-patient hospitalization or prolongation of existing hospitalization, or
 - 4) medical or surgical intervention to prevent life-threatening illness or injury or permanent impairment to a body structure or a body function.
- Led to fetal distress, fetal death or a congenital abnormality or birth defect.

This includes device deficiencies that might have led to a serious adverse event if:

- Suitable action had not been taken, or
- Intervention had not been made, or
- Circumstances had been less fortunate.

These are handled under the serious adverse event reporting.

Planned hospitalization for a pre-existing condition, or a procedure required by the CIP, without serious deterioration in health, is not considered a serious adverse event.

13.4.1. Serious adverse device effect

A serious adverse device effect is an adverse device effect that has resulted in any of the consequences characteristic of a serious adverse event.

13.4.2. Anticipated serious adverse device effect

There are no anticipated serious adverse device effects.

13.4.3. Unanticipated serious adverse device effect

An unanticipated serious adverse device effect is a serious adverse device effect which by its nature, incidence, severity or outcome has not been identified in the current version of the risk analysis report.

13.5. Medical care of subjects

Principal investigator shall ensure that adequate medical care is provided to a subject experiencing an adverse event during and after participation in the clinical investigation. All serious adverse events will be followed until a resolution is addressed.

Subjects are informed to contact investigator if any adverse event should occur during the investigation. Furthermore, investigator will inform the subjects to contact him should serious adverse events occur within one week of the subject is terminated from the study. Subjects are informed to contact their General Practitioner in case of any adverse event(s) happening later than one week of investigation termination.

The status of all ongoing adverse events is documented during site close-out.

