1.3. Other

All delegated investigation tasks from Investigator to Study Nurses will be documented in the Site Personnel Signature and Delegation List.

2. Identification and description of the investigational device

The purpose of the investigation is to obtain urodynamic data while emptying the bladder [REDACTED] and therefore, no investigational devices are being investigated.

3. Justification for the conduct of the clinical investigation

Intermittent catheterisation is the preferred method of bladder emptying for persons with spinal cord injuries and neurogenic bladder dysfunction (1). Coloplast manufactures intermittent catheters and works continuously to improve them. During the development of new intermittent catheters, lab models are used to screen new catheter prototypes.

The data from the investigation will be compared to lab data [REDACTED]

4. Investigational device and clinical investigation risks and benefits

Risks associated with the investigation may be discomfort or stinging in the urethra during the urodynamic examination and the catheterisation. Furthermore, there may be a risk of micro trauma and haematuria after catheterisation, which heals within 1-3 days. After a urodynamic examination, there may be a risk of obtaining a urinary tract infection.

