6.2.4. Subject withdrawal criteria

The subject can withdraw from the investigation at any time for whatever reason without any consequences for their future treatment outside the clinical investigation.

Investigator may withdraw a subject from the investigation at any time if they judge it to be the subject's interest.

The investigator must withdraw a subject from the investigation due to:

- Noncompliance with the CIP impacting the scientific integrity of the investigation.
- If subject's safety and wellbeing is compromised by further participation.

Withdrawn subjects will not be replaced by new subjects.

A subject who is withdrawn from the investigation, for any reason, will be encouraged to contact the investigator if problems arise that he believes are related to the investigation. A subject who has not experienced adverse events will not be followed up. For subjects who experience adverse events, see section 14. At termination, due to above reasons investigator or study nurse completes the termination form and sponsor is informed.

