6.4. Monitoring Plan

During the period of the investigation monitoring is planned and carried out by the Clinical Manager.

Before doing any review of subject data, the Clinical Manager must review the signed Informed Consent Form(s) and only monitor data from subjects with a correct signed Informed Consent Form.

The first monitoring visit at the site should be conducted as soon as reasonably possible after the first subject at the site has completed the first visit of the investigation to minimise systematic errors done by site.

Additional monitoring will be conducted in accordance to the recruitment rate:

Monitoring visit two (2) will be conducted as soon as possible after the completion of the first 15 subjects

Monitoring visit three (3) will be conducted as soon as possible after the completion of the last 15 subjects

Monitoring visit four (4), Close out visit, will be conducted as soon as possible after database lock

Written informed consent, in- and exclusion criteria and all Adverse events occurring in the investigation will be 100% verified for timely completion for all subjects enrolled in the investigation.

Investigation Site File shall be monitored for 100% completion per the Investigation File Requirement Checklist

Monitoring activities conducted by the clinical manager will be documented in the site visit report applicable to the conducted visit. A summary describing the observation(s) and actions required shall be provided as soon as reasonably possible to the investigator after the conducted monitoring visit.

The sponsor representative will have close contact to the site in the recruitment period to ensure that any concerns, problems or recruitment challenges are solved with the site in a timely manner.

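### No contact is scheduled after the IC visit, and the one-week request in Section 13.5 names only serious events, so the AE listing may miss delayed non-serious events, mainly UTI in SCI and BPH patients

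*Combined protocol and SAP*

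**What the plan says.** **Schedule.** Tables 4 and 5 end at the IC visit, which is visit 2 for the 10 healthy volunteers and visit 1 for the 20 SCI and BPH patients. AEs are registered at that visit. Section 6.3.1 then states that the man has completed the investigation and has the termination form filled in. For the patients this is also their only urodynamic examination.

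**What subjects are asked to report.** Section 13.5 has three sentences on this:
- "Subjects are informed to contact investigator if any adverse event should occur during the investigation".
- "investigator will inform the subjects to contact him should serious adverse events occur within one week of the subject is terminated from the study".
- The general practitioner is to be contacted "in case of any adverse event(s) happening later than one week of investigation termination".

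The section adds: "The status of all ongoing adverse events is documented during site close-out".

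**What the protocol expects.** Section 4 says: "After a urodynamic examination, there may be a risk of obtaining a urinary tract infection". Table 6 lists UTI as an anticipated device effect, in the 2-10% band for SCI and BPH patients and the 0-1% band for healthy volunteers. Section 13.4.2 anticipates no serious device effects.

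**What is done with AEs.** They are a safety endpoint (Section 6.1.1) and are listed on the safety population (Section 7.1). Under Section 13.6.1 the principal investigator assesses all AEs at his site, and all adverse device effects go to the sponsor within 10 days.

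**The concern.** The request for the week after the last visit covers the class of event that the protocol does not anticipate, and leaves out the class that it does. A UTI listed in Table 6 is by implication non-serious, because no serious device effect is anticipated, and Section 4 places it after the examination. A man who develops one a few days after the IC visit has no scheduled contact at which to mention it, and no sentence that clearly asks him to call about it.

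At stake is the completeness of the AE listing after catheterisation. A listing with few or no infections could be read as a finding about the procedure when it partly reflects what the men were asked to report. The gap is in data collection; Section 13.5 separately makes the investigator responsible for medical care.

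**Working it through.** The plan states no event count, rate estimate or power for AEs, so there is no figure to reproduce. The check has a textual part and a numerical part.

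**1. Which sentence covers a non-serious event in the week after the IC visit?**

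| Sentence in Section 13.5 | Events | Period |
|---|---|---|
| First | any | during the investigation |
| Second | serious only | one week from the subject's termination |
| Third (general practitioner) | any | later than one week from investigation termination |

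Only the first could cover it, and that depends on when the investigation ends:
- *Narrow reading.* It ends for each man at his IC visit. Section 6.3.1 says so for both cohorts. On this reading nothing explicit covers the event.
- *Wide reading.* It ends when the last subject finishes (Section 6.2.6). The event is then covered, but for a time that differs between men and is shortest for the last ones. A separate one-week rule for serious events would also be redundant for nearly everyone.

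The narrow reading fits the text better, but the text does not settle it. The second and third sentences also start from different points, the subject's termination and the investigation's termination.

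**2. Do other provisions close the gap?**
- The 10-day rule in Section 13.6.1 has no cut-off at termination, so a UTI that the site knows of is reportable. It does not help the site to learn of one.
- The close-out check concerns events that are already ongoing. By Section 6.4 it also comes late: "Monitoring visit four (4), Close out visit, will be conducted as soon as possible after database lock".

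**3. Size, from the protocol's own bands.** Inputs: 20 SCI and BPH patients and 10 healthy volunteers (Section 6.1); UTI bands 2-10% and 0-1% (Table 6 and the text below it).

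Expected UTIs, n × p:
- Patients: 20 × 0.02 = 0.4 to 20 × 0.10 = 2.0
- Healthy volunteers: 10 × 0 = 0 to 10 × 0.01 = 0.1

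The issue is therefore mainly one for the patients. The 0.4-2.0 is an upper figure for delayed UTIs, because it includes any same-day events and because antibiotic prophylaxis may lower it.

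The documents give no onset times, so the share c of all UTIs that reaches the investigator has to be assumed. Taking the men as independent with equal risk, the chance that at least one UTI is listed is 1 − (1 − p × c)^20:

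| Assumed share c | p = 2% | p = 10% |
|---|---|---|
| 0% | 0% | 0% |
| 25% | 1 − 0.995^20 = 9.5% | 1 − 0.975^20 = 40% |
| 50% | 1 − 0.99^20 = 18% | 1 − 0.95^20 = 64% |
| 100% | 1 − 0.98^20 = 33% | 1 − 0.90^20 = 88% |

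The low rows would apply only if most UTIs appeared after the visit and were not volunteered. The table shows sensitivity to the assumption and does not estimate c.

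**The case against.** The best defence is that Section 13.5, read as a whole, already asks for these events. Sending any adverse event later than one week to the general practitioner implies that those within the week go to the investigator, and the wide reading of the first sentence says so directly. Section 13.6.1 shows that the sponsor wants every adverse device effect. The subject information is not among the documents and may be clearer. Some lines of the IC visit are redacted, although the visit columns of Tables 4 and 5 are visible and end there. AEs are only listed, no test or comparison is planned, and no investigational device is under study.

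Part of this stands. Nothing forbids reporting a non-serious event, and one known to the site must be reported. But the implication in the general-practitioner sentence runs from a different starting point, and it competes with an explicit sentence limited to serious events. What remains unclear is what the man himself is asked to report.

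Three stronger readings are tempting, and the documents do not support them:
- *AEs registered at visit 2 in healthy men may belong to visit 1.* Symptoms and multistix are checked before the visit 2 examination, which goes ahead only if both are clear (Section 6.3.1). The four-day minimum interval is there so that micro trauma can heal (Section 6.1.4). An event that came and went between visits can be placed by its onset date.
- *Haematuria will be missed too.* Section 4 says "there may be a risk of micro trauma and haematuria after catheterisation, which heals within 1-3 days". That is a healing time and not an onset time. Haematuria beginning at catheterisation can be registered at the visit, so the Table 6 haematuria band says nothing about delayed events.
- *Men who withdraw are asked for more than men who complete.* Section 6.2.4 says that a withdrawn man "will be encouraged to contact the investigator if problems arise that he believes are related to the investigation". That is limited to problems he thinks are related, and the same section gives no follow-up to those without AEs. It is not evidence of better collection.

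**Conclusion.** The point holds as a minor one. No contact follows the IC visit, the only explicit request for the next week is limited to serious events, and the delayed effect that the protocol names, UTI, is one that it expects to be non-serious. The listing after IC may therefore be incomplete, mainly for UTI in the 20 patients, where at most 0.4 to 2.0 events are expected on the Table 6 band.

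This rests on the narrower reading of the first sentence of Section 13.5, which is the better supported but not the only possible one. It also rests on treating the Table 6 bands as per-subject risks; the documents do not say whether those bands assume antibiotics. The number of events that would actually be missed cannot be derived from the documents.

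A reader might infer that the safety assessment or the main results are compromised. They are not: the urodynamic objectives are unaffected, and no AE rate or test is planned.

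**What to change.** For data collection:
1. In the one-week request of Section 13.5, replace serious adverse events with any adverse event, counted from the subject's own last visit.
2. Reconcile the two starting points in that section, the subject's termination and the investigation's termination. No general-practitioner referral rule is proposed here.
3. State the reporting window after IC beside the AE listing, so that a short list is read against the time and method of observation.

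**Cost.** The wording change costs almost nothing beyond Ethics Committee approval of the amendment. A few more events would need recording. Attribution would stay uncertain in SCI and BPH men, who catheterise daily. Collection would still depend on self-report, so the change makes the request clear without guaranteeing a complete listing. A short telephone contact at about one week is an optional addition, at about 30 calls.
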